10.3 Additional Hypothesis Tests

The following two-sided hypothesis tests will be applied using the observed estimates for NLR and PLR as well as using the PROPROC for the partial ROC AUC:

- NLR:
 - $H_0: NLR_{IUS} = NLR_{Imagio}$ vs
 - $H_A: NLR_{IUS} \neq NLR_{Imagio}$ representing a reduction
- PLR:
 - $H_0: PLR_{IUS} = PLR_{Imagio}$ vs
 - $H_A: PLR_{IUS} \neq PLR_{Imagio}$ representing an increase
- Partial ROC AUC:
 - $H_0: pAUC_{IUS} = pAUC_{Imagio}$ vs
 - $H_A: pAUC_{IUS} \neq pAUC_{Imagio}$ representing an increase

Hierarchical testing will be applied to seek labeling claims if warranted by the pre-defined testing procedure (see Section 10.8).

10.4 Population Definition

Masses and images will be selected for use in accordance with the study protocol, inclusion and exclusion criteria.

10.5 Interim Analysis

10.5.1 Plan

The interim analysis (IA) is to re-estimate sample size to avoid running an underpowered study. The IA will be performed by an unblinded statistician. The Sponsor and all other parties will remain blinded to the results. The only communication to the sponsor will be the final sample size recommendation. The sample size may be increased up to 840 masses from the initial 480 masses in increments of 120 masses per block in order to achieve 80% power for the primary endpoint. This recommendation will be based solely on variance parameters re-estimated in the IA (but not the effect size). Thus, these IA results fall into the category of non-comparative results. Thus, the IA has negligible effect on the Type 1 error. The IA will be based on the total variance estimate (inclusive of both reader and imaging modality variations) so, the IA remains 'non-comparative' since the interim treatment effect was not used to compute the final sample size.

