10.2 Reader / Image Set Sample Size

The sample size will be based on the primary effectiveness endpoint, namely the gain in specificity for fixed 98% sensitivity. This calculation depends upon the number of image sets (one per mass) to be read, the number of readers, as well as the inter-reader variability associated with the underlying models used for analysis.

The test of the primary hypothesis is powered to detect a 10% absolute specificity advantage (superiority) as the alternative hypothesis with no specificity advantage as the null hypothesis. The primary endpoint will be evaluated in the following testable hypotheses:

$$H_0: S_{\text{Imagio}} = S_{\text{IUS}}$$

$$H_1: S_{\text{Imagio}} \neq S_{\text{IUS}}$$

where S_{Imagio} and S_{IUS} represent specificity, values associated with Imagio (IUS + OA) and IUS.

The sample size calculations conservatively assume that both readers and masses are random effects; an ANOVA model will be used to compute sample size. The sample size was computed using the following statistical software written by Stephen Hillis and entitled: Multi-Reader Sample Size Program for Diagnostic Studies [<http://perception.radiology.uiowa.edu>].

For 80% power, a two-sided hypothesis test with a two-sided 5% alpha, and 15 readers, a sample size of 854 image sets is needed to detect a 10% absolute advantage in specificity for Imagio (IUS + OA) vs IUS, assuming a fixed 98% sensitivity and the same intra- and inter-reader standard deviation observed in the Reader-1 Feasibility Study.

The supporting calculations including the software output follow:

Results for Feasibility variance estimates

User-supplied parameter or pilot-study values:

Design : factorial
Tests : nonequivalence
Readers and cases : both readers and cases random
Input values : treat as known
Alpha : 0.05
Input Format : OR variance components with error covariances
test*reader var comp : 0.00203538
Error variance : 0.03571
Cov1 : 0.01106919
Cov2 : 0.0061484
Cov3 : 0.0043063
c* : 120

User-supplied desired power, proposed readers & cases values

Desired Power : 0.8
Proposed max readers : 15
Proposed max cases : 2000
Proposed min readers : 15
Proposed min cases : 20

Corresponding OR variance components, covariances, and correlations

test*reader var comp : 0.00203538
Error variance : 0.03571
Cov1 : 0.01106919
Cov2 : 0.0061484
Cov3 : 0.0043063
r1 : 0.309974517
r2 : 0.172175861
r3 : 0.120590871

Sample Size Results

effect size :	readers :	Cases :	POWER

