0.1 :	15 :	854 :	0.801

Initially, 360 masses will be read by all readers for the purposes of performing the interim analysis to assess the sources of variation and to rerun the sample size estimate for the primary effectiveness endpoint. Neither futility nor efficacy will be assessed; this is not an adaptive design.

The sample size may be increased from the minimum of 480 image sets to a maximum of 840 image sets (7 complete blocks) in increments of 120 masses per block. All original color balance masses will be replaced with comparable masses and image sets within the final analysis from the PIONEER Pivotal overage masses.

The maximum sample size to be used for the study will be capped at 840 masses. An overage mass set will be set aside in case quality control issues are found with the images and replacement masses are needed. After excluding the pool of 840 masses and overage masses, approximately 900 masses will remain for independent SenoGram training. No masses used to train the SenoGram, will be in the pool of 840 study masses plus overage. We have removed the 29 masses from the pool of study masses which were mistakenly included from the original color balance algorithm.

Every effort will be made to identify missing reader generated data in real time. Each block of 120 masses will include 75 benign (72 benign + 3 high risk) and 45 malignant masses to represent the PIONEER study.

With the exception of masses excluded due to protocol deviations, all complete reads will be included in all analyses, consistent with an "Intention-to-Diagnose" approach.

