 13. For 80% power, a two-sided hypothesis test with a two-sided 5% alpha and 15 readers, a sample size of 854 image sets is needed; the 79% power with 840 image sets is deemed adequate to test the primary hypothesis test; the sample size was calculated using the same intra- and inter-reader standard deviation observed in the READER-01 Feasibility Study.
 14. A blinded interim analysis is planned after all readers complete the reading of the first three blocks (360 -10 Color Balance = 350 image sets). The interim analysis will only assess the reader variability associated with the primary endpoint; the sample size may be left at 480 image sets or increased up to 840 image sets based solely on the variability determined from the primary analysis.
 15. READER-01 Feasibility Study data will not be combined with the READER-02 Pivotal Study data but may be referenced in the final Pre-market Approval (PMA).
 16. Effectiveness analyses (interim and final) will be performed without the CB cases as the primary analysis. The interim analysis will be based on 350 masses without replacement while the final analysis will be based on the sample size to be determined to potentially include all or some of the 29 replacement cases.
 17. For completeness, a pre-defined subset of the PIONEER Study tables and listings will be regenerated for the subset of 480 to 840 masses using the READER-02 Pivotal Study data.
 18. For completeness, the differences which can be detected with 80% power will be calculated for the primary endpoint (specificity gain at 98% sensitivity) and for the secondary endpoint (pAUC over 95-100% sensitivity).
 19. A hierarchical testing strategy will be implemented to extend labeling by testing effectiveness in the following order: gain in specificity for fixed 98% sensitivity, decrease in NLR, gain in PLR, and gain in pAUC over 95% to 100% sensitivity where gain is the difference between the OA/US and IUS values.

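### The sample size re-estimation is said to secure 80% power, but its 840-mass cap lies below the 854 masses the plan itself requires, so the capped design has at most about 79% power and somewhat less once smaller final sizes are allowed for

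*Combined protocol and SAP*

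**What the plan says.** Protocol 10.2 and SAP 2.1.4 report the same software run. With 15 readers, two-sided 5% alpha and the Reader-01 variance components, "a sample size of 854 image sets is needed to detect a 10% absolute advantage". Both then set a limit: "The maximum sample size to be used for the study will be capped at 840 masses". The permitted final sizes are 480, 600, 720 and 840.

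Protocol 10.5.1 gives the purpose of the interim: "The interim analysis (IA) is to re-estimate sample size to avoid running an underpowered study". It and SAP 2.1.11.3 say that the number of masses may be raised from 480 to 840 so that the primary endpoint has 80% power. SAP 2.1.1 item 11 also ties the primary test to 80% power.

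SAP 2.1.1 item 13 is the only place that gives the power at the cap: "the 79% power with 840 image sets is deemed adequate". The protocol never states this figure.

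Protocol 10.5.3 and SAP 2.1.11.3 list two recommendations for the case where 840 masses are not enough, one to continue and one not to.

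**The concern.** At the planning variances, no size that the interim can recommend reaches the power it is said to secure. The cap also means that the procedure cannot respond fully to the situation that would make the study underpowered, namely a variance above the Reader-01 estimate. In the other direction, an interim variance that is low by chance can end the reads at 480, 600 or 720, where power at the planning variances is well below 79%.

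The SAP's 79% is the power of a study fixed at 840. It is not the power of the design described, in which the final size depends on a variance estimated from 350 masses and 15 readers. Neither document gives that second figure. A sponsor or regulator who takes 80% from Protocol 10.5.1 is relying on a property that the design does not have.

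**Working it through.** **Inputs** (Protocol 10.2, repeated in SAP 2.1.4)
- "For 80% power, a two-sided hypothesis test with a two-sided 5% alpha, and 15 readers, a sample size of 854 image sets is needed"; software power at 854: 0.801
- Effect: "powered to detect a 10% absolute specificity advantage (superiority) as the alternative hypothesis", so d = 0.10
- "Readers and cases : both readers and cases random"; factorial design; r = 15
- "test*reader var comp : 0.00203538"
- Error variance 0.03571; Cov1 0.01106919; Cov2 0.0061484; Cov3 0.0043063; c* = 120

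**Formulae** (Obuchowski-Rockette model with Hillis degrees of freedom, c masses)
- MS(TR) = var_TR + (c*/c)(error variance − Cov1 − Cov2 + Cov3) = 0.00203538 + (120/c)(0.02279871)
- D = MS(TR) + r(c*/c)(Cov2 − Cov3) = MS(TR) + (120/c)(15 × 0.0018421) = MS(TR) + (120/c)(0.0276315)
- Noncentrality = r d²/(2D) = 0.075/D
- Denominator df = 14 D²/MS(TR)²
- Power from the noncentral F(1, df) at alpha 0.05

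**The plan's own figures.** At c = 854, MS(TR) = 0.005239, D = 0.009122, noncentrality = 8.222, df = 42.4 and power = 0.8001 (plan: 0.801). At c = 853, power is 0.7998, so 854 is the smallest size that reaches 80%. The plan's number is reproduced.

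**Permitted sizes at the Reader-01 variances**

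| Masses | D | Noncentrality | Power |
|---|---|---|---|
| 480 | 0.01464 | 5.12 | 60.2% |
| 600 | 0.01212 | 6.19 | 68.3% |
| 720 | 0.01044 | 7.18 | 74.6% |
| 840 | 0.00924 | 8.12 | 79.5% |

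The 79.5% agrees with the SAP's 79%.

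**Power at 840 if all variance components are higher by the same factor** (assumption)

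| Increase | Power at 840 | Masses needed for 80% |
|---|---|---|
| +10% | 75.6% | 970 |
| +20% | 72.0% | 1,094 |
| +25% | 70.2% | not computed |
| +50% | 62.3% | 1,521 |

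**Power of the rule.** The documents do not give the re-estimation algorithm in enough detail to reproduce it, so this step rests on assumptions. Take the true variances to be those of Reader-01, estimate MS(TR) from 350 masses with 14 df, hold the error covariances at their planning values, and choose the smallest listed size that reaches 80%. About 41.7% of studies then stop at 720. The other 58.3% go to 840, including 45.8% in which 840 is judged not sufficient and reads are assumed to continue. Average power is 0.417 × 0.746 + 0.583 × 0.795 = 0.311 + 0.463 = 77.5% approximately. This mixture ignores any dependence between the interim variance and the final test. A full simulation of the same simplified rule gave 77.7%, against 79.4% simulated at a fixed 840. Letting the error components be re-estimated as well, with assumed noise of 10% to 30%, changes the spread of final sizes but leaves average power at about 77%.

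**The case against.** **The gap at 840 is small and disclosed.** This stands. At the planning variances the shortfall from 80% is about half a point, the SAP states 79% and accepts it, and 840 would reach 80% if all components were only about 1.2% lower. A reader might infer that the sample size calculation is wrong or the shortfall hidden. The documents support neither. The 80% attached to 854 in Protocol 10.2 is correct, and 854 and the cap appear in the same section. The 80% in Protocol 10.1 is a design target and makes no claim about 840.

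**The procedure can raise the size.** This also stands. A reader might infer that the re-estimation can only shorten the study. The documents start from 480, and moving from 480 to 840 raises power from 60.2% to 79.5%. The size can only come down relative to 840 or 854.

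**The simulated split is not the plan's.** This stands for the split. Protocol 10.5.1 refers to a total variance estimate, whereas the simplified rule re-estimates only the reader-by-modality part. Under that rule 480 and 600 can never be chosen, and about 32% of the component estimates are truncated at zero. The shares stopping at 720 or told that 840 is insufficient should not be quoted as properties of this trial. The average power is less sensitive: it stayed at about 77% when the error components were allowed to vary.

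**The plan foresees that 840 may not suffice.** It does, so 80% is not guaranteed in every outcome. But those options do not correct the stated aim, and no numerical threshold defines a reasonable chance of significance. Any use of the option not to continue would lower power below the figures above, which assume that reads go on to 840.

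**Conclusion.** The 80% statement is wrong where it is attached to the capped, re-estimated design: Protocol 10.5.1, SAP 2.1.11.3 and SAP 2.1.1 item 11. If the Reader-01 variances hold, power is at most 79.5%, and roughly 77% to 78% once the possibility of smaller final sizes is counted. The first figure follows from the plan's inputs. The second depends on an assumed re-estimation rule and is only an indication.

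The difference from 80% is modest. The more consequential point is that the cap leaves no room for a variance above Reader-01, where power at 840 falls to about 72% (+20%) or 70% (+25%) if all components rise together. The planning components are scaled to 120 cases and entered as known, so a higher true variance cannot be ruled out.

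**What to change.** Leave the 854-mass, 80% calculation in Protocol 10.2 and SAP 2.1.4 unchanged.

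In Protocol 10.5.1, SAP 2.1.1 item 11 and SAP 2.1.11.3, replace the 80% statement with wording such as: *Power is at most 79% at the 840-mass cap if the Reader-01 variances hold, and somewhat lower once re-estimation is allowed for.* The lower figure should come from the sponsor's simulation of the rule it will actually use, not from the approximation given here.

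In the same places, state that the interim chooses a final size between 480 and 840 and cannot restore power if the variance exceeds Reader-01. Add the power at 840 for variances 25% and 50% above planning (70% and 62% here, with all components scaled together).

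The cost is wording, a short simulation and a slightly less favourable stated power. The number of masses, the readers and the primary test do not change.

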10.5.2 Methodology

The sole IA goal is to compute the final sample size based on the primary endpoint. The sample size re-estimation (SSRE) will be performed without any adaptation. SSRE will be conducted to detect the pre-planned 10% absolute advantage in specificity for fixed 98% sensitivity, given that this is an established criterion agreed upon with FDA. The standard deviation (from reader as a random effect) is not known. There will be no preplanned or performed assessments for futility, stopping for early efficacy, dropping readers, altering the pre-planned 10% effect hypothesis, or any other adaptation. Therefore, this is classic SSRE.

Huang and Chen (1) references this application as distinct from their discussion of adaptive designs. Our IA is based entirely on non-comparative data, that is, no information about treatment effects were incorporated into the decision process. For this SSRE situation (a non-comparative interim), it can be shown that performing analyses at the conventional one-sided 0.025 significance level has a negligible effect on the Type 1 error probability (FDA Guidance

on Adaptive Trials (2), Wittes (3), Kieser and Friede (4), Friede and Kieser (5), among others). Wittes advises that the alpha spend is small when the observed variance is less than the assumed variance (as per the interim analysis) without accounting for imaging modality. Huang and Chen advise that the alpha spend is small when the conditional power exceeds 60% which is the case when a 10% delta is assumed; any delta effect would further reduce the reader variance. Thus, the alpha spend for conducting the planned interim analysis is small.

From a testing perspective, the conclusions should hold in recognition that the p-value is a Z-score whether derived from a one-sample or a two-sample test independent of the model used (Huang or Hillis). All alpha adjustment depends on a linear combination of Z-scores (6) for respective Z-scores prior to and after the pre-planned interim analysis. Thus, first principles all lead to the conclusion that the alpha spend is small enough to ignore. Our estimate is that the alpha spend is no more than 0.01% under the given conditions. The minimal alpha spend derives from the abundant two-sample literature to apply to our paired sample setting with no published literature.

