10.5.3 Timing

The single blinded interim analysis is planned once 360 (360-10 color balance masses=350) completed image sets are read by each reader and the data become available. The interim analysis will be performed by an independent, unblinded third party statistician who will make recommendations below to Seno Medical Inc. based on the results from this initial cohort of masses:

1. Sample Size Calculation:

___ One additional block is required (480 masses) OR

___ Two additional blocks are required (600 masses) OR

___ Three additional blocks are required (720 masses) OR

___ Four additional blocks are required (840 masses) OR

___ Four additional blocks (840 masses) are not sufficient but reads should continue because there is a reasonable chance to reach statistical significance based on the conditional power assuming the alternative hypothesis holds.

___ *Four additional blocks (840 masses) are not sufficient, reads should not continue because there is not a reasonable chance to reach statistical significance based on the conditional power assuming the alternative hypothesis holds.*

To maintain blinding to the interim results, no specific results from the interim analysis will be shared by the unblinded party performing the analysis with Seno or any other study participant, and only one of the above recommendations will be provided. Seno retains the right to accept, not accept, or modify any recommendation concerning changes to conduct of the study.

There are no plans to stop the study early for benefit or a positive outcome on the basis of the interim analysis results. No alpha will be spent to perform this interim analysis since this analysis is for sample size re-estimation only (1). Under no circumstances will the alternative hypothesis be modified as a result of this analysis. The final analysis will include the results from the n=360 (360-10 color balance masses=350) interim analysis.

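### The stated alpha cost of the interim (no more than 0.01%) has no derivation and fails if the sample size is re-estimated from the OR variance components; the plan does not settle which variance estimator is used

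*Combined protocol and SAP*

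**What the plan says.** - **Final test (protocol 10.2).** The plan puts the requirement at 854 masses for a 10-point gain. It gives the settings as "For 80% power, a two-sided hypothesis test with a two-sided 5% alpha, and 15 readers". The study is capped at 840, where SAP 2.1.1 item 13 accepts 79% power.
- **Interim rule (protocol 10.2, 10.5).** All readers complete 360 masses, of which 350 are analysed. The final size is then set at 480, 600, 720 or 840 to reach 80% power, using re-estimated variance only and a gain fixed at 10 points. The interim data stay in the final analysis.
- **Alpha cost.** Protocol 10.5.2 and SAP 2.1.11.3: "Our estimate is that the alpha spend is no more than 0.01% under the given conditions". Both add that this carries two-sample results over to a paired setting without published literature. Protocol 10.5.3: "No alpha will be spent to perform this interim analysis since this analysis is for sample size re-estimation only".
- **Support offered.** One condition is that the observed variance is below the assumed variance. The other is that "the alpha spend is small when the conditional power exceeds 60% which is the case when a 10% delta is assumed". The SAP adds a conditional-power range of 0.37 to 0.80, which it links to the promising zone.
- **Variance estimator.** Protocol 10.5.1 names a total variance covering both reader and modality variation. Protocol 10.5.4 names an overall SD. SAP 2.1.1 item 14 names reader variability only. SAP 2.1.9 Table 1 assigns the re-estimation to the OR-DBM sample size program, whose inputs in protocol 10.2 are separate components.

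**The concern.** The primary endpoint, and the labeling hierarchy behind it, are tested at an unadjusted 5% on the strength of this figure. A variance-only rule can still raise the error. When the interim variance happens to be low, the study is made shorter, and the same 15 readers and 350 masses then feed the final standard error. That standard error has few degrees of freedom (14 for test-by-reader), so in short studies it is too small on average.

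The conditional-power argument also looks misplaced. Type I error is defined under no gain, and conditional power depends on an interim gain that the plan says is not used. A regulator could repeat the calculation and find a stated number that the design does not have.

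**Working it through.** **1. Inputs (protocol 10.2).** "test*reader var comp : 0.00203538"; "Error variance : 0.03571"; "Cov1 : 0.01106919"; Cov2 0.0061484; Cov3 0.0043063; c* = 120; 15 readers; gain 0.10.

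**2. Reproducing the plan's figures.** With N masses, error terms scale by 120/N:

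- MS(TR) = 0.00203538 + (Error − Cov1 − Cov2 + Cov3) × 120/N = 0.00203538 + 0.02279871 × 120/N
- Denominator = MS(TR) + 15 × (Cov2 − Cov3) × 120/N = MS(TR) + 0.0276315 × 120/N
- Denominator df = 14 × (Denominator / MS(TR))²
- Noncentrality = 15 × 0.10² / (2 × Denominator)

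At N = 854: MS(TR) = 0.005239, denominator = 0.009122, df = 42.4, noncentrality = 0.075/0.009122 = 8.22, power = 0.800 (stated 0.801). At N = 840 power is 0.795 (stated 79%). At 480, 600 and 720 it is 0.602, 0.683 and 0.746. The plan's sample size is confirmed.

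**3. Type I error of the component-based rule.** Simulation under no gain, with normal case-level contributions and the same 15 readers throughout. Components are estimated from 350 masses. The smallest of 480/600/720/840 with re-estimated power of at least 80% is taken, otherwise 840. The pooled data are then tested at two-sided 5%. The excess is measured against the same test at fixed sizes, weighted by how often each size is chosen (about 5.06% to 5.08%). Monte Carlo standard error is about 0.002 to 0.005 points.

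| True variances ÷ plan | Share ending at 480 / 600 / 720 / 840 | Error, component rule | Excess (points) | Error, lumped rule | Excess (points) |
|---|---|---|---|---|---|
| 0.6 | 0.61 / 0.19 / 0.08 / 0.12 | 5.22% | +0.15 | 4.54% | −0.54 |
| 0.7 | 0.33 / 0.31 / 0.13 / 0.24 | 5.26% | +0.19 | 4.61% | −0.46 |
| 0.8 | 0.05 / 0.43 / 0.17 / 0.36 | 5.20% | +0.14 | 4.77% | −0.30 |
| 1.0 | 0 / 0.05 / 0.35 / 0.61 | 5.13% | +0.07 | 4.96% | −0.11 |
| 1.2 | 0 / 0 / 0.05 / 0.95 | 5.08% | +0.01 | 5.06% | −0.01 |

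The shares are for the component rule. Outside the table, its excess is +0.015 at 0.4, +0.07 at 0.5, +0.10 at 0.9 and 0.00 at 1.5. Changing only the reader component (0 to 1.5 times plan) at the planned error terms gives +0.055 to +0.08. From 0.5 to 1.0 times plan, the excess is roughly 6 to 19 times 0.01 points. Halved for one side, it is about 0.03 to 0.10, still above 0.01.

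**4. Lumped rule.** Here the interim mean square pools modality (1 df) with test-by-reader (14 df): [14 × MS(TR) + 15 × d²/2] / 15, where d is the interim gain. A large chance gain then lengthens the study and is diluted, so the error does not exceed the fixed-size level. This formula is one assumed construction, because the plan gives none.

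**5. Conditional power under no gain, planning variances.** At 350 masses the denominator is 0.00203538 + (0.02279871 + 0.0276315) × 120/350 = 0.019326. The variance of the gain is 2 × 0.019326/15 = 0.002577 (SE 5.08 points), and the information is I₁ = 388. The information at the final size is 512 for 480 masses and 812 for 840, so the fractions are 0.758 and 0.478. Then

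CP = Φ{[d × I₁ + 0.10 × (I_N − I₁) − 1.96 × √I_N] / √(I_N − I₁)}.

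- N = 480: CP = 0.60 needs d = (2.82 + 44.36 − 12.41)/388 = 9.0 points. Under no gain P(Z > 9.0/5.08) is about 4%.
- N = 840: d = (5.21 + 55.84 − 42.36)/388 = 4.8 points. Under no gain P(Z > 4.8/5.08) is about 17%.

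With t critical values the probabilities are about 3% and 15% (6% for 600, 10% for 720).

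**6. The variance condition.** When the assumed variance is true, the interim estimate falls below it in 54% of trials.

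**The case against.** The strongest reply is that the rule is not the component-based one. Protocol 10.5.1 includes modality variation, 10.5.4 speaks of an overall SD, and the plan cites work on blinded sample size adjustment. On that reading there is no inflation. This stands. It is why one cannot say that the rule, followed exactly, inflates the error. It does not rescue the 0.01% figure, which is underived on either reading, and it leaves SAP Table 1 pointing to a program that takes separate components.

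Second, the excess is not general: it almost vanishes at 1.2 times plan or more. The simulation also leaves out the last recommendation in 10.5.3, to stop reading. That option has no threshold. If it were binding at re-estimated power below 60% (an assumption), the excess would be +0.17 at 0.7 times plan and −0.22 at plan. Both points stand.

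Third, a reader might infer that every supporting condition fails under the null. The documents do not support that, since the variance condition is met about half the time. The 60% may also loosely mean unconditional power, which is 60.2% at 480 masses. That is a different quantity, and it does not bound Type I error either.

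Fourth, the model is approximate. The endpoint is specificity read from fitted ROC curves, non-normality was not examined, and the fixed-size test already sits at 5.06% in this model. This limits trust in the second decimal of the level. The excess is a comparison within one model, so it is less exposed.

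**Conclusion.** The concern holds in a limited form. The 0.01% bound has no derivation and conflicts with the statement that no alpha is spent. It fails if the interim re-estimates OR components and true variances are about 0.5 to 1.0 times plan: about +0.07 points at plan, and at most about +0.19 points (5.26%) near 0.7 times plan. With a lumped variance that includes modality, the error was at or below its fixed-size level throughout the range examined. The sign of the effect therefore turns on an estimator that the plan describes inconsistently.

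The conditional-power argument is unsound as support. It needs an interim gain that the plan says is not used, and at the planning variances it holds in only about 3% to 17% of interims under no gain. The promising-zone range is likewise defined by conditional power.

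A reader might infer that Type I error is out of control; it is not. Under the component rule, studies that end below 840 reject a true null in roughly 5.7% to 6.6% of cases in the low-variance settings simulated. That rate is conditional on a low interim variance and is not the Type I error. The plan's general description of the cost as negligible largely survives; its number and its reasoning do not.

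These results assume normal case-level contributions, 15 complete readers, no binding stop, and 0.01% read as percentage points.

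**What to change.** 1. State in protocol 10.5 and SAP 2.1.11.3 exactly which variance estimator the interim uses, whether the modality effect is in it, and how it enters the sample size program.
2. Delete the 0.01% figure and the conditional-power and promising-zone justification.
3. Replace them with the simulated Type I error of that exact rule over a range of true variances, for example 0.4 to 1.5 times plan, with a stated treatment of the stop recommendation.
4. Reconcile protocol 10.5.1, 10.5.2, 10.5.3 and 10.5.4 with SAP 2.1.1 item 14, Table 1 and 2.1.11.3.

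The cost is one simulation and a wording change. A fixed replacement figure, such as 0.1 to 0.2 points, would not be sound, because the cost varies with the true variance and the estimator. Testing at a slightly lower level such as 0.048 is optional. In simulations of the component rule it gave about 4.9% to 5.1%, for about half a point of power (77.6% to 77.1% at the planning variances). It is unnecessary if the variance is lumped.
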